10.3.1.2. General Considerations for the OLE Period

Unless otherwise specified, the OLE period starts at the first injection of study treatment at Week 16 (Visit 7) and ends on the date of Week 104 (Visit 29) or the ETV (between Weeks 16 and 104).

For the efficacy and health outcomes analyses, baseline is defined as the last available value before the first injection in the OLT period and, in most cases, will be the value recorded at Week 0 (Visit 2).

Unless otherwise specified, for the safety analyses during the OLE period, baseline is defined as the last available value before first injection of either ixekizumab or adalimumab in the OLE period. In most cases, this will be the measure recorded at Week 16 (Visit 7).

Safety and efficacy data for participants in the OLE period adalimumab switchers population will be summarized separately using descriptive statistics without inferential statistics. Safety baseline for switchers is defined as the last available value before first injection of ixekizumab or adalimumab in the OLE period.

All efficacy and safety data collected will be summarized using descriptive statistics.

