6.1.1. Populations for Analyses

For analysis purposes, populations are defined based on the different treatment period in [Table RHCG.6.1](#). A disposition of the study analysis population and a listing of the analysis population will be provided as well.

Table RHCG.6.1. Analysis Populations

Population	Period	Description
Enrolled		All patients who sign informed consent.
ITT population	OLT	All patients, even if the participant does not take the assigned treatment, does not receive the correct treatment, or otherwise does not follow the protocol. Unless otherwise specified, efficacy and health outcomes analyses will be conducted on the ITT Population during the OLT period. Patients will be analyzed according to the treatment to which they were assigned.
OLE period population	OLE	All patients who receive at least 1 dose of either treatment in OLE.
OLE period adalimumab switchers (switchers)	OLE	Patients initially randomized to adalimumab who switch to ixekizumab in the OLE period
OLT safety population	OLT	All patients who received at least 1 dose of either treatment product in OLT.
LTE safety population	LTE	All participants who received at least 1 dose of ixekizumab in the LTE period
PTFU period population	PTFU	Safety analyses for the Post-Treatment Follow-Up Period will be conducted on the Post-Treatment Follow-Up Period population, defined as all randomized patients who received at least 1 dose of study treatment at any time during the study period, and have entered the Post-Treatment Follow-Up Period. Patients will be analyzed according to the treatment in which they were assigned.

Abbreviations: ITT = Intend-To-Treat; OLE = Open-Label Extension; OLT = Open-Label Treatment; LTE = Long-Term Extension; PTFU = Post-Treatment Follow-Up.

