6.1.2.2.1. OLE Period Population

Baseline for OLE Period Population will be defined as the last available value on or before the first injection of study treatment in the OLT Period at Week 0 (Visit 2) for efficacy, health outcomes. For patients without a date of first study drug injection at Week 0 (Visit 2), the last nonmissing assessment on or before randomization date will be used.

Unless otherwise specified, for the safety analyses during the OLE period, baseline is defined as the last available value on or before first injection of either ixekizumab or adalimumab in the OLE period. In most cases, this will be the measure recorded at Week 16 (Visit 7). For treatment-emergent adverse events (TEAEs), baseline are adverse events (AEs) which started prior to the study drug injection at Week 16 (Visit 7).

Additional Population Information

For patients who were initially randomized to adalimumab at Week 0 and were switched to ixekizumab by their investigators, only data up to the time of initiation of a switch to ixekizumab will be included in the OLE Period analyses using the OLE Period Population. These patients will be considered nonresponders to categorical assessment per the NRI method after the switch to ixekizumab. Data collected after switch to ixekizumab therapy has started will be summarized separately for the Switcher Population (Section [6.1.2.2.2](#)).

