6.1.2.2.2. OLE Period Switcher Population

For efficacy analyses on the Switcher Population, baseline is defined as the last nonmissing assessment recorded on or prior to the date of first study drug injection at Week 0 (Visit 2). For safety analyses, baseline is defined as the last nonmissing assessment prior to the first injection of a switch to ixekizumab. For TEAEs during a switch to ixekizumab, baseline is the event ongoing just prior to the first injection of a switch to ixekizumab.

For the Switcher Population, efficacy measures after initiation of a switch to ixekizumab will be summarized without inferential statistics.

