6.1.2.4. General Considerations for the PTFU Period

For the safety analyses during the PTFU period, baseline is defined as the last nonmissing assessment on or prior to entering the PTFU period, that is, on or prior to Week 104 (Visit 29), or ETV.

Safety data will be summarized using descriptive statistics without inferential statistics by the study treatment the patient was receiving immediately prior to entering PTFU period.

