6.12.1. Extent of Exposure

Duration of exposure to study treatment (defined as time since first injection of study treatment in days) will be summarized by treatment group during the OLT Period and the OLE Period.

The duration of exposure during the **OLT Period for the Safety Population** will be calculated as:

(Date of last study visit in OLT Period – Date of first injection of study treatment + 1)

The duration of exposure on initially assigned treatment for the **OLE Period Population** will be calculated as:

Date of last visit on initially assigned treatment – Date of first dose in OLE Period + 1

The duration of exposure during the **OLE Period** for the OLE Switcher Population will be calculated as:

(Date of last study visit in OLE Period – The first date of switch to ixekizumab + 1)

The duration of exposure during the **LTE Period** for LTE Safety population will be calculated as:

(Date of last study visit in LTE Period – Date of first injection of study treatment + 1)

Descriptive statistics will be provided for patient days of exposure and the frequency of patients falling into the following different exposure ranges (that is, only the exposure ranges that fall within the treatment period will be presented) will be summarized:

- $>0, \geq 7 \text{ days}, \geq 14 \text{ days}, \geq 30 \text{ days}, \geq 60 \text{ days}, \geq 90 \text{ days}, \geq 120 \text{ days}, \geq 183 \text{ days}, \geq 365 \text{ days.}$
- $>0 \text{ to } <7 \text{ days}, \geq 7 \text{ to } <14 \text{ days}, \geq 14 \text{ to } <30 \text{ days}, \geq 30 \text{ to } <60 \text{ days}, \geq 60 \text{ to } <90 \text{ days}, \geq 90 \text{ to } <120 \text{ days}, \geq 120 \text{ to } <183 \text{ days}, \geq 183 \text{ to } <365 \text{ days}, \geq 365 \text{ days.}$

Overall exposure for each treatment group within the OLT Period and the OLE Period for respective populations will also be summarized in total patient years. This will be calculated as follows:

Exposure in patient years = Sum of duration of exposure with the defined treatment period (for all patients in treatment group) / 365.25.

A listing of study drug exposure will also be provided.

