The number and percentage of patients, and the number of events (where applicable) will be presented, by treatment group for each treatment period, separately. When the SOC is presented, events will be ordered by decreasing frequency in the ixekizumab dose group, within SOC. When the SOC is not presented, the events will be ordered by decreasing frequency in the overall group followed in the order of ixekizumab Q4W then adalimumab Q2W. For incidence counts, each patient will be counted only once within each Preferred Term and within each SOC. Percentages will be based on the number of patients in a particular treatment group. For events that are gender-specific, the denominator and computation of the percentage will include only patients from the given gender.

The following summary tables will be provided for the OLT Period (Safety Population), OLE Period (OLE Period Population and OLE Switcher Population), and LTE Period (LTE Safety Population):

- An overview summary of AEs
- TEAEs, by SOC and Preferred Term
- TEAEs, by Preferred Term
- TEAEs by maximum severity, by SOC and Preferred Term

The following summary tables will be provided for the PTFU Period (PTFU Population):

- FAEs, by Preferred Term

By-patient listing of all TEAEs will be provided.

If a partial or completely missing AE start date/time or end date/time is present the following imputation rules will be utilized in the analysis:

- For the start date:
 - If year, month, and day are missing, then use the earlier of the patient's first visit date or the consent date.
 - If either month or month and day are missing, then use January 1.
 - If only day is missing, impute the first day of the month.

- For the start time:
 - Impute as 23:59
- For the end date:
 - If year, month, and day are missing, then use the patient's last visit date in the follow-up period.
 - If either month or month and day are missing, then use December 31.
 - If only day is missing, then use the last day of the month.
 - The imputed date will not be beyond the patient's last visit date in the follow-up period.
- For the end time:
 - Impute as 23:59.
- If there is any doubt, the event will be flagged as treatment-emergent or follow-up emergent according to the corresponding study period. If a follow-up emergent event was already counted as treatment-emergent during the prior treatment period, it will not be counted as a follow-up emergent event.

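### Two PTFU attribution rules put every adalimumab-to-ixekizumab switcher under different drugs, and as written Week 16 switchers can dilute the adalimumab OLE adverse-event percentages

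*SAP*

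**What the plan says.** **Follow-up.** For the PTFU population, SAP Table RHCG.6.1 states: "Patients will be analyzed according to the treatment in which they were assigned". Protocol Table RHCG.10.1 says the same. SAP 6.1.2.4 instead summarises follow-up safety "by the study treatment the patient was receiving immediately prior to entering PTFU period". SAP 6.12 and Protocol 10.3.1.4 agree with 6.1.2.4.

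**OLE.** The OLE Period Population is "All patients who receive at least 1 dose of either treatment in OLE". The period opens with the Week 16 injection (SAP 6.1.2.2). Adalimumab participants without a JIA ACR30 response at Week 16 are switched, and responders may switch (SAP 5.1). For switchers, "only data up to the time of initiation of a switch to ixekizumab will be included in the OLE Period analyses" on this population; later data go to the Switcher Population (SAP 6.1.2.2.1). For adverse events, "Percentages will be based on the number of patients in a particular treatment group" (SAP 6.12.2.1). The disposition summary counts Switchers as a category inside the OLE Period Population (SAP 6.5). The exposure rule in SAP 6.12.1 for that population begins "The duration of exposure on initially assigned treatment for the".

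**Switcher safety baseline.** Protocol 10.3.1.2: "Safety baseline for switchers is defined as the last available value before first injection of ixekizumab or adalimumab in the OLE period". SAP 6.1.2.2.2: "baseline is defined as the last nonmissing assessment prior to the first injection of a switch to ixekizumab".

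**The concern.** Adalimumab is the only concurrent reference in the trial, with about 20 participants, and its safety results will be read as plain percentages with no inferential analysis behind them. Two features could distort those percentages.

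First, if the table wording for PTFU is programmed, events that arise after a participant's ixekizumab treatment are reported under adalimumab. This can reach anyone who switches in the OLE or who moves to ixekizumab for the LTE, so potentially most of the reference arm.

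Second, keeping switchers in the OLE denominator makes sense for responder endpoints, where they count as failures under NRI. In an adverse-event table the same person would count as event-free. Participants who started on ixekizumab continue it in the OLE, so they are not affected and any bias runs one way.

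A smaller matter is that the protocol and the SAP start the switcher's safety baseline at different times.

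**Working it through.** The documents give no OLE adalimumab denominator or event rate, so there is no plan figure to reproduce here.

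**Step 1: PTFU column under each rule.**

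| Treatment history | By assignment (SAP Table RHCG.6.1, Protocol Table RHCG.10.1) | By treatment before PTFU (SAP 6.1.2.4 and 6.12, Protocol 10.3.1.4) |
|---|---|---|
| Ixekizumab throughout | ixekizumab | ixekizumab |
| Adalimumab, never switched | adalimumab | adalimumab |
| Adalimumab, switched in the OLE | adalimumab | ixekizumab |
| Adalimumab to Week 104, then ixekizumab in the LTE | adalimumab | ixekizumab |

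The rules disagree for every switcher and for nobody else.

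**Step 2: what a Week 16 switcher contributes to the OLE Period Population.** The first OLE dose is ixekizumab, which is enough for entry. The period starts with that injection and data stop at the switch, so there are no countable OLE adverse events. Exposure by the SAP 6.12.1 formula is Week 16 date minus Week 16 date plus 1, or 1 day.

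**Step 3: effect on adalimumab incidence percentages, if tabulated by initially assigned drug.** With N adalimumab participants entering the OLE and s switching at Week 16:

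reported % = true % among continuers × (N-s)/N

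Inputs:
- N = 20 (SAP 5.2), assuming all 20 enter the OLE.
- Response of 71%: an assumption, taken from the Week 12 figure that Protocol 3.2 gives for adalimumab in an ERA study. A range of 50% to 80% is shown.
- Mandatory switches: s = 20 × (1 - response). At 71%, 20 × 0.29 = 5.8, rounded to 6.

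| Assumed response | s, mandatory only | Factor | s if about 25% of responders also switch at Week 16 (assumed) | Factor |
|---|---|---|---|---|
| 50% | 10 | 0.50 | 12 | 0.40 |
| 60% | 8 | 0.60 | 11 | 0.45 |
| 71% | 6 | 0.70 | 10 | 0.50 |
| 80% | 4 | 0.80 | 8 | 0.60 |

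At a factor of 0.70, a true incidence of 60% among continuers is shown as 42%, and 20% as 14%.

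**Step 4: effect on patient-years.** A continuer who stays the full 88 weeks has 616 + 1 = 617 days. With 6 switchers at 1 day each, (14 × 617 + 6)/365.25 = 23.67 patient-years; without them, 14 × 617/365.25 = 23.65. With 12 switchers, 13.55 against 13.51, a change of less than 0.3%. Exposure-adjusted rates are therefore not diluted.

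**Step 5: laboratory displays.** Change from baseline in SAP 6.12.4 needs at least one post-baseline result. The cytopenia shift tables in 6.12.4.1 need a minimum post-baseline value. The hepatic elevation counts in Table RHCG.6.16 are for patients with a post-baseline value. A Week 16 switcher has none before the switch and drops out of these displays.

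**Step 6: switcher baseline.** For a participant who switches at Week 32, the protocol baseline is the value before the Week 16 injection and the SAP baseline is the value before the Week 32 injection. A change that arose on adalimumab between those visits is post-baseline under the protocol and part of baseline under the SAP. For a Week 16 switcher the two coincide.

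**The case against.** The main objection is to the OLE point. No sentence says that OLE Period Population safety tables keep Week 16 switchers in an adalimumab column. SAP 6.12 divides OLE safety into before and after the switch, each with its own population, and Protocol 5.1.3 treats those switched after the OLT as a separate group. On that reading a Week 16 switcher has no before-switch period and would be left out. The nonresponder sentence in SAP 6.1.2.2.1 concerns categorical efficacy and fixes no safety denominator. This has force: grouping by initial drug is an inference from SAP 6.1.2.2.1, 6.5 and 6.12.1. But nothing removes these participants from the population, so a programmer following the definitions would retain them.

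It is also fair to say that SAP 6.12.1 already plans patient-years by treatment group and SAP 6.5 tabulates switchers, so a reader could work back to the continuer denominator. The adverse-event tables themselves remain counts and percentages.

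On PTFU, the two SAP sections written for that analysis agree with each other, so misattribution occurs only if the table wording is followed. 'Assigned' might also be read as including reassignment, since Protocol 7.8.2 speaks of adalimumab participants being assigned to ixekizumab after Week 104. The SAP does not say so, and the conflict stands as text in both documents.

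On the baseline, the SAP already uses the switch date and separately defines the TEAE baseline for switchers, so little would go wrong in practice.

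Finally, the reference arm is described mainly as context for efficacy, all safety summaries are descriptive, and the randomised comparison in the OLT is untouched. These points limit the importance; they do not remove the inconsistency.

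**Conclusion.** The PTFU conflict is explicit in both documents, and following the assignment rule would place ixekizumab-period follow-up events under adalimumab for every switcher. The OLE dilution follows from the stated definitions if the population is tabulated by initially assigned drug. Its size then depends on the number of Week 16 switchers, which the documents do not give; both the response rates and the optional-switch share in the table are assumptions. It applies to subject-incidence percentages for TEAEs, SAEs and AE discontinuations. The baseline mismatch is minor.

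A reader might infer that the plan makes adalimumab look safer across all OLE safety output, or that follow-up events are certain to be charged to the wrong drug. The documents do not support either. Most laboratory displays need a post-baseline value, patient-year rates barely move, the OLE grouping is implied rather than stated, and the PTFU sections of the SAP already use the last treatment. The primary endpoint is not affected.

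**What to change.** 1. In SAP Table RHCG.6.1 and Protocol Table RHCG.10.1, replace analysis by assigned treatment for the PTFU population with analysis by the treatment last received before PTFU, matching SAP 6.1.2.4 and 6.12 and Protocol 10.3.1.4.
2. In SAP 6.1.2.2.1 or 6.12.2.1, state the OLE adverse-event denominator: the adalimumab column holds participants with at least one adalimumab dose in the OLE, with data to the first ixekizumab dose. Keep post-switch data in the Switcher tables.
3. Align the switcher safety baseline in Protocol 10.3.1.2 with SAP 6.1.2.2.2.

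The cost is SAP wording and table shells plus short protocol corrections, with no new data. The downside is a smaller adalimumab denominator in the OLE adverse-event tables, for example 14 instead of 20 under the 71% assumption with mandatory switches only. The changes should be made before the OLE and PTFU tables are programmed.

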6.1.2. General Statistical Considerations

For all treatment periods, change from baseline will be calculated as the postbaseline value minus the baseline value. Percent change from baseline is defined as: 100 times the change from baseline divided by baseline. Percent improvement from baseline is calculated as: the positive

percent change from baseline if a higher value postbaseline means improvement from baseline; and as the negative percent change from baseline if a lower value postbaseline means improvement from baseline. If the baseline value is missing for a particular variable, then the change from baseline and the percent improvement from baseline will not be calculated.

6.1.2.1. General Considerations for the OLT Period

The OLT period starts at the first injection of study treatment at Week 0 (Visit 2) and ends prior to the first injection of study treatment at Week 16 (Visit 7) or the ETV (between Weeks 0 and 16). Efficacy and health outcomes data collected in the OLT period will be summarized for intent-to-treat (ITT) population without inferential statistics.

Efficacy baseline will be defined as the last available value on or before the first injection at Week 0 (Visit 2) for efficacy and health outcomes. In most cases, this will be the measure recorded at Week 0 (Visit 2). For efficacy measures, if the patient does not take any injection, the last available value on or prior to randomization date will be used.

For safety analyses using a baseline period, the baseline period is defined as the time from Visit 1 to the date/time of the first injection at Week 0 (Visit 2).

6.1.2.2. General Considerations for the OLE Period

Unless otherwise specified, the OLE period starts at the first injection of study treatment at Week 16 (Visit 7) and ends on the date of Week 104 (Visit 29) or the ETV (between Weeks 16 and 104).

6.1.2.2.1. OLE Period Population

Baseline for OLE Period Population will be defined as the last available value on or before the first injection of study treatment in the OLT Period at Week 0 (Visit 2) for efficacy, health outcomes. For patients without a date of first study drug injection at Week 0 (Visit 2), the last nonmissing assessment on or before randomization date will be used.

Unless otherwise specified, for the safety analyses during the OLE period, baseline is defined as the last available value on or before first injection of either ixekizumab or adalimumab in the OLE period. In most cases, this will be the measure recorded at Week 16 (Visit 7). For treatment-emergent adverse events (TEAEs), baseline are adverse events (AEs) which started prior to the study drug injection at Week 16 (Visit 7).

Additional Population Information

For patients who were initially randomized to adalimumab at Week 0 and were switched to ixekizumab by their investigators, only data up to the time of initiation of a switch to ixekizumab will be included in the OLE Period analyses using the OLE Period Population. These patients will be considered nonresponders to categorical assessment per the NRI method after the switch to ixekizumab. Data collected after switch to ixekizumab therapy has started will be summarized separately for the Switcher Population (Section [6.1.2.2.2](#)).

6.1.2.2.2. OLE Period Switcher Population

For efficacy analyses on the Switcher Population, baseline is defined as the last nonmissing assessment recorded on or prior to the date of first study drug injection at Week 0 (Visit 2). For safety analyses, baseline is defined as the last nonmissing assessment prior to the first injection of a switch to ixekizumab. For TEAEs during a switch to ixekizumab, baseline is the event ongoing just prior to the first injection of a switch to ixekizumab.

For the Switcher Population, efficacy measures after initiation of a switch to ixekizumab will be summarized without inferential statistics.

6.1.2.3. General Considerations for the LTE Period

The LTE period starts at the first injection of ixekizumab at Week 104 (Visit 29) and ends after the injection of ixekizumab at Week 264 (Visit 69) or at ETV (between Weeks 104 and 264).

All safety data will be descriptively summarized using the LTE safety population. For safety analyses using a baseline period, the baseline period is defined as the time from Visit 1 to date/time of the first injection in the LTE period.

Efficacy and health outcomes data collected in the LTE period will be summarized for the ITT population who entered the LTE period without inferential statistics.

All safety data will be descriptively summarized using the LTE safety population, defined as ITT participants who receive at least 1 dose of ixekizumab in the LTE period.

